1. INTRODUCTION

The purpose of this reporting and analysis plan (RAP) is to describe the analyses to be included in the Clinical Study Report for Protocol: 212548/02. Note that GSK3739937 is also known as VH3739937 and will be referred to as VH3739937 for the remainder of this document.

Protocol Revision Chronology:		
Protocol	Date	Notes
212548/00	20-APR-2020	Original
212548/01	11-JUN-2020	Amendment 01 was generated to remove Sodium Stearyl Fumarate from the placebo formulation, to clarify administration for study interventions and maintenance of the blind. Revisions were made to the study eligibility criteria and safety assessments in response to the FDA's feedback and to mitigate the potential risks for study conduct during the COVID-19 pandemic. Given the absence of benefit to study participants, the exclusion criteria and the criteria for individual subject discontinuation, dose escalation and stopping the study were revised to be more conservative. Revisions were made to improve accuracy of the study risk assessment and the pharmacokinetic analyses.
212548/02	16-MAR-2021	Updates made following acquisition of clinical pharmacology data in Part 1, the Single Ascending Dose (SAD) 10 mg, 30 mg, 80 mg, 160 mg, 320 mg and 640mg treatment periods and Multiple Ascending Dose (MAD) Cohort 3; 25 mg to: 
• extend the period of post dosing assessment to include outpatient visits in the study;• include a higher dose SAD treatment period (800 mg);• revise the duration of dosing in MAD Cohort 5 (100 mg); and• inclusion of an additional MAD Cohort 6 (500 mg) to evaluate weekly oral dosing. Part 3 of the study was included to evaluate the relative bioavailability (RBA) of

		VH3739937 when administered as VH3739937 powder-in-a-bottle (PiB) or as VH3739937 100 mg Tablet under fasted and fed (moderate fat) conditions.
--	--	---

2. SUMMARY OF KEY PROTOCOL INFORMATION

2.1. Changes to the Protocol Defined Statistical Analysis Plan

There were no changes or deviations to the originally planned statistical analysis specified in most recent version of the protocol Amendment 2 (212548/02) [(Dated: 16-Mar-2021)] which introduced Part 3 (relative bioavailability and food effect).

2.2. Study Objective(s) and Estimand(s) / Endpoint(s)

[figure not shown]
Objectives	Endpoints
Primary Objectives	Primary Endpoints

 • To investigate the safety and tolerability of VH3739937 following single and repeated daily and weekly oral administration in healthy participants (Part 1 & 2) • To assess the safety and tolerability of VH3739937 following single oral administration in healthy participants under fasted or fed (moderate calorie and fat) conditions (Part 3) • To evaluate the relative bioavailability (RBA) of VH3739937 powder in bottle (PiB) versus VH3739937 tablet and the effect of food on the PK of VH3739937 tablets and VH3739937 PiB (Part 3) 	
VH3739937 safety parameters:
 
 • Adverse events; post baseline values and changes over time of clinical laboratory evaluations (haematology, clinical chemistry, urinalysis), vital signs, and ECG parameters from pre-dose values (Part 1, 2, and 3) • Derived PK parameters for VH3739937, as data permits: Part 3 (single dose): $AUC_{(0-24)}$, $AUC_{(0-\infty)}$, C_{max},
Secondary Objectives	Secondary Endpoints

 • To describe the PK profile of VH3739937 following single (Part 1 and 3) and repeated daily and weekly oral administration in healthy participants (Part 2), as data permits 	
Derived PK parameters for VH3739937, as data permits:
 
 • Part 1 (single dose): $AUC_{(0-24)}$, $AUC_{(0-t)}$, $AUC_{(0-\infty)}$, C_{max}, C_{24}, t_{max}, t_{lag}, $t_{1/2}$, C_{last}, t_{last}, CL/F • Part 2 (repeated once daily [QD] dose):

Objectives	Endpoints
	
 ○ Day 1: $AUC_{(0-24)}$, C_{max}, C_{24}, t_{max}, t_{lag} ○ Day 14 (Cohorts 3 and 4): $AUC_{(0-\tau)}$, C_{max}, $C\tau$, t_{max}, $t_{1/2}$, and CL/F ○ Day 14 (Cohort 5): $AUC_{(0-\tau)}$, C_{max}, $C\tau$, t_{max} ○ Day 18 (Cohort 5): $AUC_{(0-\tau)}$, C_{max}, $C\tau$, t_{max}, $t_{1/2}$, and CL/F ● Part 2 (repeated once weekly [QW] dose, as data permits: 
 ○ Day 1 (Cohort 6): $AUC_{(0-168)}$, C_{max}, C_{168}, t_{max}, t_{lag} ○ Day 8 (Cohort 6): $AUC_{(0-168)}$, C_{max}, C_{168}, t_{max} ○ Day 15 (Cohort 6): $AUC_{(0-t)}$, C_{max}, $C\tau$, t_{max}, $t_{1/2}$, and CL/F ● Part 3 (single dose): $AUC_{(0-24)}$, $AUC_{(0-\infty)}$, C_{max}, C_{24}, t_{max}, t_{lag}, $t_{1/2}$, C_{last}, t_{last}, CL/F

 ● To examine dose proportionality following single and repeated doses of VH3739937 (Part 1 & 2), as data permits 	
Derived PK parameters for VH3739937, as data permits:
 
 ● Part 1 (single dose): $AUC_{(0-\infty)}$, C_{max}. ● Part 2 (repeated dose): $AUC_{(0-\tau)}$, C_{max}, $C\tau$

 ● To predict the accumulation from single dose data (Part 1) and assess accumulation of VH3739937 after repeat doses (Part 2 at steady state), as data permits 	
Accumulation indices for PK parameters for VH3739937, as data permits:
 
 ● Part 1 (single dose): predicted accumulation ratio R_p based on AUC ● Part 2 (repeated dose): observed accumulation ratios: $RAUC(0-\tau)$, $R(C_{max})$, $R(C\tau)$

 ● To assess time to steady-state of VH3739937 (Part 2) 	
Derived PK parameters for VH3739937, as data permits:
 
 ● Part 2 (repeated dose): 
 ○ Cohorts 3 and 4: Pre-dose concentrations on Day 2-14 ○ Cohort 5: Pre-dose concentrations on Day 2-18
Exploratory Objectives	Exploratory Endpoints

 ● To assess the exposure response relationship between VH3739937 and safety parameter, including QTcF following single and repeated administration (Part 1 & 2) 	
 ● Change-from-baseline QTcF ($\Delta QTcF$)

Objectives	Endpoints

• To collect plasma and urine samples for analysis of metabolites of VH3739937	
• Metabolites of VH3739937 in plasma and urine. The analyses will be conducted and reported separately from this protocol.

• To characterize renal excretion of VH3739937, as data permits	
• Urinary recovery of VH3739937 ($Ae[0-x]$), $Ae[0-\tau]$ and $Ae[0-t]$) and renal clearance (CLR)

• To collect duodenal bile for analysis of metabolites of VH3739937 (Part 2, Cohort 5 only)	
• Metabolites of VH3739937 in duodenal bile. The analyses will be conducted and reported separately from this protocol

- Note: The exploratory endpoints may be analyzed once VH3739937 clinical development continues.

2.3. Study Design

Overview of Study Design and Key Features	
	
placebo (PBO) for 14 consecutive days (cohorts 3 and 4), or for 18 consecutive days (cohort 5). Participants in Cohort 6 will receive one dose per week for 3 consecutive weeks.
 
 • The duration of dosing in Cohort 5 is to support up to 18-day dosing as an oral lead in for the future SAD and MAD studies of the long acting formulation of VH3739937. This duration is to potentially allow the identification of any early drug hypersensitivity reactions (HSR) which may occur before the administration of the long acting formulation. • In each escalating dose cohort, 7 participants will be randomized to receive VH3739937 and 3 participants will be randomized to receive PBO 
Part 3 (RBA/FE)
 
 • Part 3 is a randomized, open-label, single-dose, 3-period crossover Cohort 7 to compare the RBA of the PiB formulation of VH3739937 with the tablet formulation and to assess the effect of food on the safety, tolerability and PK of the tablet formulation in healthy participants. • In Part 3, approximately 18 participants will be treated to ensure that 12 evaluable participants complete Cohort 7.
Dosing	
Part 1 (SAD):
 
 • In Part 1 participants will receive a single dose of VH3739937 • Dose escalation in Part 1 will be determined by the Dose Escalation Committee based on the double-blind (sponsor-unblinded) safety data and the PK data from the current and previous dose(s). • Dose escalation will not exceed approximately 3-fold between doses up to approximately the predicted minimally effective dose and will not exceed 2-fold thereafter. • Dose escalation in Part 1 will require (from the current dosing group) at least 24 hours of safety and PK data from 4 participants receiving active drug. Dose escalation will be guided by safety and the SAD PK stopping criteria (see Protocol Section 8). • Due to the alternating dosing periods between Cohort 1 and Cohort 2, a participant in either cohort will receive the next dose after approximately 3 or 4 weeks. 
Part 2 (MAD):
 
 • In Part 2 participants will receive a single dose of VH3739937 each day for either 14 days (Cohorts 3 and 4) 18 days (Cohort 5), or once weekly for 3 weeks (Cohort 6) • Part 2 (MAD) of the study will be initiated once the single dose safety and preliminary PK data for the anticipated minimally effective dose has been evaluated in the SAD. • The potential minimally effective dose for VH3739937, noted as 25 mg, is anticipated to be that which is predicted to provide a steady state C_{trough} \geq 0.258 μg/mL in 95% of participants and will be re-estimated based on the PK data collected in the early doses in Part 1. • Dose escalation in Part 2 will be determined by the VH/GSK study team and the PI based on the double-blind (sponsor-unblinded) safety and PK data (minimally up to 24 h post Day 14 dose) from the current and previous dosing cohort(s). Specifically, 14 days of safety and PK data (minimally up to 24 h post Day 14 dose) from a minimum of five participants in current cohort receiving active drug will be required for dose escalation

Overview of Study Design and Key Features																																	
	
Part 3 (RBA/FE)
 
 Participants will receive each of the following treatments administered as 1 treatment per period: 
 Treatment A: VH3739937 PiB, 100 mg (single dose oral suspension of VH3739937 dispersion) administered under moderate fat conditions (reference) Treatment B: VH3739937 Tablet, 100 mg (single dose given as a 100 mg tablet(s)) administered under moderate fat conditions (test) Treatment C: VH3739937 Tablet, 100 mg (single dose given as 100 mg tablet(s)) administered under fasted conditions (reference). To ensure adequate washout, there will be at least 24 days between each dose of study intervention, with an allowance window of 4 hours (i.e., 24 days minus 4 hours) to allow flexibility in scheduling participants for dosing at the clinic. 																																
Time & Events	
 Refer to Appendix 2: Schedule of Activities 																																
Treatment Assignment	
Part 1 (SAD):
 
 Participants in either Cohort 1 or Cohort 2 will be assigned to 1 of the 3 treatment sequences in a cross-over, and each participant will receive placebo once. 
  
 Cohort 1	Period 1	Period 2	Period 3	
   
 Sequence 1	Placebo	Dose 3	Dose 5	
 
 Sequence 2	Dose 1	Placebo	Dose 5	
 
 Sequence 3	Dose 1	Dose 3	Placebo	
  
 
  
 Cohort 2	Period 1	Period 2	Period 3	
   
 Sequence 1	Placebo	Dose 4	Dose 6	
 
 Sequence 2	Dose 2	Placebo	Dose 6	
 
 Sequence 3	Dose 2	Dose 4	Placebo	
  
 
 When the 800 mg dose is evaluated, 9 new participants, who were not previously exposed to any dose of VH3739937 will be enrolled in the study. Six participants randomized to receive VH3739937 and 3 participants will be randomized to receive placebo. 
Part 2 (MAD):
 
 In Cohorts 3 to 5, 10 participants per cohort (active/PBO=7/3) will receive a once-daily dose of VH3739937 or PBO for 14 days (Cohort 3 and 4) or 18 days (Cohort 5) In Cohort 6, 10 participants (active/PBO=7/3) will receive a once-weekly dose of 500 mg VH3739937 or PBO over the course of 14 days (Doses on Day 1, 8, and 15) 	Cohort 1	Period 1	Period 2	Period 3	Sequence 1	Placebo	Dose 3	Dose 5	Sequence 2	Dose 1	Placebo	Dose 5	Sequence 3	Dose 1	Dose 3	Placebo	Cohort 2	Period 1	Period 2	Period 3	Sequence 1	Placebo	Dose 4	Dose 6	Sequence 2	Dose 2	Placebo	Dose 6	Sequence 3	Dose 2	Dose 4	Placebo
Cohort 1	Period 1	Period 2	Period 3																														
Sequence 1	Placebo	Dose 3	Dose 5																														
Sequence 2	Dose 1	Placebo	Dose 5																														
Sequence 3	Dose 1	Dose 3	Placebo																														
Cohort 2	Period 1	Period 2	Period 3																														
Sequence 1	Placebo	Dose 4	Dose 6																														
Sequence 2	Dose 2	Placebo	Dose 6																														
Sequence 3	Dose 2	Dose 4	Placebo																														

Overview of Study Design and Key Features	
	
Part 3 (RBA/FE):
 
 • In Part 3 participants will randomly be assigned to receive a random sequence of the following treatments: 
 ○ Treatment A: VH3739937 PiB, 100 mg (administered as oral suspension under moderate fat conditions (reference)) ○ Treatment B: VH3739937 Tablet, 100 mg (single dose given as a 100 mg tablet(s)) administered under moderate fat conditions (test) ○ Treatment C: VH3739937 Tablet, 100 mg (single dose given as 100 mg tablet(s)) administered under fasted conditions (reference) • In Part 3, participants will be assigned to one of three sequences according to a Latin square design. The three sequences are: 
 ○ A/B/C ○ B/C/A ○ C/A/B
Interim Analysis	
 • All preliminary safety, tolerability, and available PK data will be reviewed internally at ViiV/GSK prior to each dose escalation. Safety data (labs, vital signs, ECG, AEs, SAEs) will be reviewed by the PI/Sub-I and ViiV/GSK study team after completion of each dose level. • Dose escalation can only occur after DEC has found that the safety and PK profiles are supportive to proceed with the evaluation of the next higher dose level (See Protocol Section 4.3.6 Dose Escalation Committee).

2.4. Statistical Analyses

2.4.1. Part 1 (SAD) and 2 (MAD)

The main purpose of Parts 1 and 2 of study is to assess the safety, tolerability and PK of single and repeated oral doses of VH3739937 in healthy volunteers. A mixed model will be used to assess whether participants in Part 2 achieved steady state as described in Section 8.1.5.1.

2.4.2. Part 3 (RBA)

The purpose of Part 3 is to evaluate the relative bioavailability and food effect of two differing formulations of VH3739937 (tablet vs. powder in a bottle). For the assessment of relative bioavailability of formulation and food effect the log-transformed PK parameters will be analysed as data permits using separate mixed effect models with fixed effect terms for fed vs. fasted and tablet vs PiB. Participant will be treated as a random effect in each model. Point estimates and their associated 90% CIs will be calculated for the difference in $AUC_{(0-24)}$, $AUC_{(0-\infty)}$, and C_{max} for the tablet vs PiB and fed vs fasted comparisons. The point estimates and their associated 90% CIs will then be back-transformed to provide point estimates and 90% CIs for the ratios of tablet vs PiB and fed vs fasted in PK parameter values on the original scale.

No formal statistical hypothesis will be tested. The mixed model will be used to estimate relative bioavailability and food effect but will not be used to justify statistical bioequivalence.

3. PLANNED ANALYSES

3.1. Interim Analyses

There will be no formal interim analysis; however, all preliminary safety, tolerability, and available pharmacokinetic data will be reviewed internally at the Dose Escalation Committee (ViiV/GSK) prior to each dose escalation or administration and according to the dose escalation charter. Safety data (labs, vital signs, ECG, AEs, SAEs) will be reviewed by the PI/Sub-I and ViiV/GSK study team after completion of each dose level. Dose escalation can only occur after PI/Sub-I and ViiV/GSK study team has found that the safety, PK profiles are supportive to proceed with the evaluation of the next highest dose level.

At each dose, the Bayesian probability of an individual exceeding the Cmax threshold in Part 1 and the Bayesian probability of an individual exceeding the AUC threshold in Part 2 will be calculated and compared with 50%. This will be used to help selection of the next dose together with safety and tolerability data. The Bayesian probability will be based on Whitehead's model shown below [Whitehead, 2001] using non-informative prior for model parameters.

$$y_{ij} = \theta_1 + \theta_2 d_{ij} + s_i + \epsilon_{ij}$$

Where y_{ij} is log-PK of i -th participant to j -th dose, d_{ij} is j -th log-dose administered to i -th participant. θ_1 and θ_2 are population intercept and slope, respectively. s_i is random effect of i -th participant and ϵ_{ij} is random error of i -th participant in j -th dose.

When intra-participant variability cannot be estimated during PK predictions in Part 1 (i.e., early on in the study when there is not sufficient information to estimate intra-participant variability) and for conducting prediction of all doses in Part 2, the same Whitehead's model will be used for Bayesian probability calculations as below.

$$y_i = \theta_1 + \theta_2 d_i + \epsilon_i$$

Where y_i is log-PK of i -th participant, d_i is the log-dose administered to i -th participant. θ_1 and θ_2 are population intercept and slope, respectively and ϵ_i is random error of i -th participant.

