4.3.4. Part 2 (MAD) Starting Dose and Dose Escalation

The initial dose in the MAD (Cohort 3) was approximately equal to the likely minimally effective dose, re-estimated at 25 mg based on the clinical PK data following oral administration of the suspension formulation collected in the early doses of Part 1. Dose escalation in the MAD will not exceed 2-fold between daily dosing cohorts 4 and 5 and will be governed by both safety and MAD PK stopping criteria (see Section 7.1.4 and Section 7.1.5). Based on emerging PK data in Part 1, the once weekly (QW) dosing Cohort 6 will be dosed at 500 mg. Given different assumptions for the between participant AUC variability (%CVb) and the current human PK prediction, the probability of any participant AUC(0- τ) in the MAD above 96.2 $\mu\text{g}/\text{mL}$, the LOAEL exposure in rat, are illustrated in [Table 8](#). Similarly, the probability of any participant AUC(0-24) which cover the maximum exposure in the MAD Cohort 6 above 96.2 $\mu\text{g}/\text{mL}$ is illustrated in [Table 9](#).

Table 8 Probability of any MAD participant (AUC(0- τ) $> 96.2 \mu\text{g}^*\text{h}/\text{mL}$) for potential QD doses

AUC variability	Potential VH3739937 QD MAD Doses		
	25 mg	50 mg	100 mg
25	0	0	<0.001
35	0	0	0.003
50	0	<0.001	0.028

Note: 1, %CVb: between-participant coefficient of variation

Table 9 Probability of any MAD participant (AUC(0- τ) >96.2 $\mu\text{g}^*\text{h}/\text{mL}$ and (Cmax >21 $\mu\text{g}/\text{mL}$) for 500 mg QW dose

AUC variability (%CVb ¹)	Cmax Variability (%CVb ¹)	Any Participant (AUC >96.2 $\mu\text{g}^*\text{h}/\text{mL}$ or Cmax >21 $\mu\text{g}/\text{mL}$)
25	25	0

Note: 1, %CVb: between-participant coefficient of variation

Given the results in the tables above, it is unlikely that any subject exceeds the safety thresholds in the QD or QW MAD portions of the study.

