7.1.4. PK Stopping Criteria for SAD and MAD

In the SAD, the PK stopping criteria are based on mitigating any potential for Cmax mediated effects on ECG parameters. There were no ECG or other CV effects in a good laboratory practice (GLP) single-dose CV study in telemeterized dogs (Cmax = 9.82 $\mu\text{g}/\text{mL}$) and a 1-month GLP study in dogs (Cmax = 39.8). The stopping criteria is conservatively based on lower Cmax in the CV study in telemeterized dogs where there were no CV effects (9.82 $\mu\text{g}/\text{mL}$), equivalent to 21 $\mu\text{g}/\text{mL}$, when adjusted for protein binding. Protein binding is higher in human (93%) compared to dog (85%). If safety or PK stopping criteria are not met for the current/prior doses, dose escalation in Part 1 (SAD) will be stopped in the event that the Bayesian predicted probability is $>50\%$ that any participant's Cmax for the next subsequent dose will exceed 21 $\mu\text{g}/\text{mL}$ (the SAD PK stopping criteria).

In the MAD, the PK stopping criteria are based on AUC exposures where VH3739937-related microscopic findings were observed in the stomach of rats and dogs in the GLP 1-month oral toxicity studies. Corresponding Cmax exposures are expected to be below 21 $\mu\text{g}/\text{mL}$. A NOAEL was identified for microscopic findings in the stomach of rats at 10 mg/kg/day and a LOAEL in rats was identified at 40 mg/kg/day. A NOAEL for microscopic findings in the stomach of dogs was not identified and the LOAEL in dogs was 3 mg/kg/day. At the LOAEL in rats and dogs, VH3739937 was well tolerated and resulted in minimal, reversible single cell necrosis of parietal cells and chief cells. Exposure at the LOAEL in rats was AUC = 96.2 $\mu\text{g}^*\text{h}/\text{mL}$ and in the dog was AUC = 51.9 $\mu\text{g}^*\text{h}/\text{mL}$. The LOAEL in rats was chosen as the PK stopping criteria, and exposure is approximately 4-fold higher than the AUC in rats at the NOAEL dose of 10 mg/kg/day. The selection of the higher LOAEL AUC from the two preclinical species arises from the need to achieve sufficiently high exposures for cardiodynamic assessment of the TQT prolongation risk and mitigate the need for a TQT study. In the absence of data on the effect of intrinsic and extrinsic factors on the PK of VH3739937, and at the time of study initiation, the typical targeted doses were ~ 4 x the minimal predicted efficacious dose.

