9.5. Interim Analyses

There will be no formal interim analysis; however, all preliminary safety, tolerability, and available pharmacokinetic data will be reviewed internally at the Dose Escalation Committee (ViiV/GSK) prior to each dose escalation or administration and according to the dose escalation charter. Safety data (labs, vital signs, ECG, AEs, SAEs) will be reviewed by the PI/Sub-I and ViiV/GSK study team after completion of each dose level. Dose escalation can only occur after PI/Sub-I and ViiV/GSK study team has found that the safety, PK profiles are supportive to proceed with the evaluation of the next highest dose level.

At each dose, the Bayesian probability of an individual exceeding the Cmax threshold in Part 1 and the Bayesian probability of an individual exceeding the AUC threshold in Part 2 will be calculated and compared with 50%. This will be used to help selection of the next dose together with safety and tolerability data. The Bayesian probability will be based on Whitehead's model shown below [Whitehead, 2001] using non-informative prior for model parameters.

$$y_{ij} = \theta_1 + \theta_2 d_{ij} + s_i + \epsilon_{ij} \quad [1]$$

Where y_{ij} is log-PK of i -th participant to j -th dose, d_{ij} is j -th log-dose administered to i -th participant. θ_1 and θ_2 are population intercept and slope, respectively. s_i is random effect of i -th participant and ϵ_{ij} is random error of i -th participant in j -th dose.

When intra-participant variability cannot be estimated during PK predictions in Part 1 (i.e., early on in the study when there is not sufficient information to estimate intra-participant variability) and for conducting prediction of all doses in Part 2, the same Whitehead's model will be used for Bayesian probability calculations as below.

$$y_i = \theta_1 + \theta_2 d_i + \epsilon_i \quad [2]$$

Where y_i is log-PK of i -th participant, d_i is the log-dose administered to i -th participant. θ_1 and θ_2 are population intercept and slope, respectively and ϵ_i is random error of i -th participant.

Bayesian model Operating Characteristics (OC)

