In this part, we want to explore the operating characteristics of the possibility of escalating to the 800 mg dose in the SAD portion of the study. Given different assumptions of with-in and between participant Cmax variability (CV%), and assuming dose proportionality (slope=1), data for 1000 trials were simulated based on Whitehead's model [1]. Each simulated trial contains Cmax values for 6 subjects on treatment for doses ranging from 10 mg to 640 mg in SAD cohort 1 and cohort 2.

For each simulated trial, we fit the mixed effect Bayesian model based on mode [1]. Using the following procedure, we calculated the Bayesian probability of an individual exceeding the Cmax threshold:

10,000 iterations were simulated in the MCMC procedure. In each iteration, we obtained the estimated parameters $\hat{\theta}_1, \hat{\theta}_2, \hat{s}_i$ ($i = 1, 2, \dots, 6$) and $\hat{\sigma}^2$ (the estimated standard deviation of ϵ_{ij}). Based on the estimation, a random sample for each subject, which represented the simulated exposure in the 800 mg dose, was drawn from the distribution $N(\hat{\theta}_1 + \hat{\theta}_2 \times 800 + s_i, \hat{\sigma}^2)$. We counted the number of iterations N with any simulated exposure exceeding the Cmax threshold $\log(21)$. The Bayesian probability was calculated as $1 - \frac{N}{10,000}$.

For each trial, the Bayesian probability of the 800 mg dose exceeding the Cmax threshold of log(21) was calculated and compared with different thresholds (40%, 50% or 60%). Results showed that all simulated trials had a probability less than 40%, 50%, and 60% in situations with high variability (%CVw = 50, %CVb = 50) as well as scenarios with low variability (%CVw = 12.5, %CVb = 25). These results indicate that the probability of escalating to 800 mg in the SAD is high.

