Additional simulations were conducted to determine the probability of escalating to 100 mg during the Part 2 of the study (MAD QD dosing). 1000 simulated trials were produced for each value of %CVb (25, 35, and 50), using a predicted 24-hour steady state AUC of 39.8 $\mu\text{g}^*\text{h}/\text{mL}$. More detailed information may be found in the IB Supplement [GlaxoSmithKline Document Number 2021 [RPS_CLIN_004025](#)]. For each trial, the Bayesian probability of the 100 mg MAD QD dose producing an 24 hour steady state AUC above log(96.2) was calculated. This value was compared to potential evidence thresholds of 40%, 50%, and 60%. **Table 15** shows the probability of a simulated trial having a Bayesian predictive probability of exceeding the AUC safety threshold of log(96.2) less than the various threshold values under the chosen values of CVb.

Table 15 Percentage of simulated trials of 100 QD dosing with Bayesian predicted probability of 24hr steady state AUC under safety threshold of log(96.2) across probability thresholds

AUC Variability	Probability Threshold		
	40%	50%	60%
25	0.995	0.999	1
35	0.934	0.967	0.986
50	0.791	0.880	0.927

These results indicate that the probability of escalating to 100 mg during the MAD QD dosing portion of the study is high.

Finally, simulations were performed to assess the probability of any participant having an 24 hour steady state AUC above log(96.2) or a Cmax above log(21) during the weekly MAD dosing portion of the study. It is anticipated that a 500 mg weekly dose will produce a steady state maximum daily AUC of 31.2 $\mu\text{g}^*\text{h}/\text{mL}$. Under this assumption, 1000 simulated trials were produced for each value of %CVb (25, 35, 5). Each simulated trial included 7 participants dosed at 500 mg. No simulated trial produced any participant who had either an AUC above log(96.2) or a Cmax above log (21). Therefore, the probability of a subject exceeding the safety threshold during the weekly dosing portion of the study is low.

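### Protocol 9.5 prints the complement of the exceedance probability and an unlogged dose, and Table 8 prints near one-participant risks under an any-participant title

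*SAP*

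**What the plan says.** The rule is in protocol 7.1.4. Part 1 escalation stops if the Bayesian predicted probability is above 50% "that any participant's Cmax for the next subsequent dose will exceed 21" µg/mL. Part 2 has the same form, with any participant's AUC(0-τ) against 96.2 µg·h/mL, the rat LOAEL exposure.

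Protocol 9.5 and SAP 3.1 describe the calculation in one shared sentence. For the single-dose part, the quantity named is "the Bayesian probability of an individual exceeding the Cmax threshold in Part 1". For the repeat-dose part, the sentence says that "the Bayesian probability of an individual exceeding the AUC threshold in Part 2 will be calculated and compared with 50" percent.

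The operating-characteristics part of protocol 9.5 reports a simulation for 800 mg. "We counted the number of iterations N with any simulated exposure exceeding the Cmax threshold" log(21). The draw is centred on θ1 + θ2 × 800 + s_i, and the probability is printed as 1 - N/10,000. The next paragraph names the result: "the Bayesian probability of the 800 mg dose exceeding the Cmax threshold of log(21) was calculated". It reports that every simulated trial fell below 40%, 50% and 60%, at both low and high variability. For the MAD, the same section takes "the Bayesian probability of the 100 mg MAD QD dose producing an 24 hour steady state AUC above" log(96.2) and gives the share of trials below each cut-off in Table 15.

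Table 8 in protocol 4.3.4 is titled "Probability of any MAD participant" with AUC above 96.2. At CV 25, 35 and 50% it prints <0.001, 0.003, 0.028 for 100 mg and 0, 0, <0.001 for 50 mg. The text then concludes that "it is unlikely that any subject exceeds the safety thresholds in the QD or QW MAD portions of the study".

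**The concern.** The 9.5 step is the only place in either document where the counting behind the 50% comparison is written out. N counts iterations in which someone exceeds the limit, so N/10,000 is the probability of exceeding and 1 - N/10,000 is the probability that nobody does. Model [1] defines d as log-dose, so the draw should use log(800). Anyone who takes this step as the template for the live calculation would program the wrong quantity.

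Table 8 has a different fault. Its title and the sentence after it concern a whole cohort, while its entries look like the risk for one person. With 7 active participants, a small per-person risk is roughly multiplied by 7.

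At stake is the quantitative PK stop in a first-in-human study of healthy volunteers. It is used together with safety data, the clinical stopping criteria and the dose escalation charter.

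**Working it through.** **Inputs.** Limits 21 µg/mL and 96.2 µg·h/mL (7.1.4). Active participants: 6 at 800 mg (4.1) and 7 per MAD cohort (4.1). Predicted AUC 39.8 at 100 mg and 22.7 at 50 mg, both medians (Table 11). Predicted median Cmax 1.60 at 800 mg (4.3.3). CV 25, 35, 50% (Table 8). Exposure is assumed log-normal and participants independent.

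**1. Table 8.** Take σ = √ln(1 + CV²). For one participant p = 1 - Φ(ln(96.2/median)/σ), and for any of 7 the probability is 1 - (1 - p)^7. At 100 mg ln(96.2/39.8) = 0.883. At CV 50%, σ = 0.472, z = 1.868, p = 0.031, and any of 7 is 1 - 0.969^7 = 0.197.

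| 100 mg | CV 25% | CV 35% | CV 50% |
|---|---|---|---|
| Table 8 as printed | <0.001 | 0.003 | 0.028 |
| One participant, median 39.8 | 0.0002 | 0.005 | 0.031 |
| Any of 7, median 39.8 | 0.001 | 0.033 | 0.197 |
| One participant, mean 39.8 | 0.0001 | 0.003 | 0.018 |
| Any of 7, mean 39.8 | 0.001 | 0.020 | 0.117 |

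For the printed 0.003 and 0.028 to be any-of-7 values, the median AUC would have to be about 31 and 27.5. At 50 mg and CV 50%, one participant gives 0.001 and any of 7 gives 0.008, against the printed <0.001.

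**2. The 800 mg step, by hand.** With slope 1 and median 1.60 at 800 mg, θ1 = ln 1.60 - ln 800 = 0.470 - 6.685 = -6.21. The printed draw is then centred at -6.21 + 800 ≈ 794 on the log scale, against log(21) = 3.04. Every draw exceeds, so N = 10,000 and 1 - N/10,000 = 0. At this intercept the slope would have to be below (3.04 + 6.21)/800 ≈ 0.012 to change that, so for any realistic data the answer is 0.

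**3. The 800 mg step, by simulation.** Model [1] was fitted by Gibbs sampling with vague priors: Table 7 design, slope 1, 1,000 trials per setting.

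| Draw at | Probability | CVw/CVb 50/50 | CVw/CVb 12.5/25 |
|---|---|---|---|
| log(800) | N/10,000 | mean 0.003, max 0.15 | max 0 |
| log(800) | 1 - N/10,000 | min 0.85 | min 1.00 |
| 800 | N/10,000 | 1.00 in every trial | 1.00 in every trial |
| 800 | 1 - N/10,000 (as printed) | 0 in every trial | 0 in every trial |

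Either slip alone contradicts the reported result. Correct code and both slips together each reproduce it, so the reported result cannot show which was run.

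**4. Which event does Table 15 use?** Model [2] was simulated with flat priors and 7 predicted participants. The data layout is not stated, so several were tried. At CV 50% the printed shares below 40, 50 and 60% are 0.791, 0.880 and 0.927. Any of 7 gives 0.61–0.81, 0.73–0.92 and 0.82–0.97; one participant gives 0.97–1.00 throughout; the any-of-7 complement gives 0.08–0.28 at the 50% cut-off. A second set of layouts gave 0.60–0.78 at 40%, just short of the printed 0.791, so the match is to the event and its direction and is not exact.

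**5. How far apart are the two readings of the wording?** A 50% limit on one person equals 1 - 0.5^7 = 99.2% for any of 7 (98.4% for any of 6). The any-participant limit of 50% equals 1 - 0.5^(1/7) = 9.4% per person (10.9% with 6).

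**6. Cohort 6.** Protocol 7.1.4 names AUC(0-τ) for this weekly cohort as well, and SAP 8.1.5.1.2 sets τ to 168 h there. From Table 11, AUC(0-168) at 500 mg is at least 31.3 + 144 × 0.429 = 93, and about 144 with a log-linear fall from 1.5 to 0.429. Any of 7 against 96.2 is then 0.98 to 1.00, a literal stop. With the 24-hour AUC of 31.3 it is 0.000, 0.003 and 0.060 at CV 25, 35 and 50%.

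**The case against.** The strongest reply is that this is editorial. The 9.5 step reports a finished simulation and is not the live algorithm. With a predicted median of 1.60 against a limit of 21, its conclusion cannot be in doubt. That stands: the slips are probably misprints, and the corrected result supports the same conclusion.

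On Table 8, CV 50% lies above the sponsor's own prediction. Table 11 gives an upper bound of 62.0 around 39.8. Its interval label is inconsistent (90% in the row, 95% in the note). Under log-normality the implied CV is about 27% or 23%, with any-of-7 risk about 0.004 or 0.0003. So the statement that an exceedance is unlikely holds at the predicted variability. The one-participant reading is also inferred: neither the median nor the mean input matches both printed cells exactly. These points limit the consequence, but any-of-7 values are further from the printed 0.003 and 0.028 under either input.

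A reader might infer that SAP 3.1 sets a looser, single-person rule. On that reading the chance of stopping before 100 mg at CV 50% would fall from the 12.0% implied by Table 15 to between 0 and 1.7%. The documents do not support this: 9.5 works the same phrase through as any simulated exposure, 7.1.4 says any participant, and Table 15 fits that event. The wording is ambiguous and no more.

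A reader might also infer that the weekly cohort fails its own rule. The text introducing Table 9, Table 11 note f and the weekly simulation in 9.5 all show that a 24-hour AUC was intended, and SAP 8.1.5.1.2 sets τ for the accumulation ratio. The gap is in the wording of 7.1.4.

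**Conclusion.** Two printed items are wrong as written. The 9.5 step computes the probability that nobody exceeds, at an unlogged dose, and returns 0 for any realistic data. Table 8 understates the any-participant risk at 100 mg and CV 50%: 0.028 is printed, against 0.197 with 39.8 as a median or 0.117 as a mean, about 7 or 4 times as large. The single-person wording and the Cohort 6 AUC definition are ambiguities that the rest of the protocol resolves.

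It would go too far to say that a dose decision was made with an inverted or loosened rule. No document shows that, and the charter is not among the documents. No planned single-dose or daily escalation changes: the largest corrected Table 8 value is 0.197, and the largest corrected 800 mg value is about 0.15, both well under 50%.

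These figures assume log-normal exposure, independent participants, the predicted values in 4.3.3 and Table 11, vague priors, and assumed layouts for Table 15.

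**What to change.** 1. Protocol 9.5, 800 mg simulation: change 800 to log(800) in the draw and 1 - N/10,000 to N/10,000, and confirm that the code did this.
2. Protocol 4.3.4, Table 8: retitle it as the probability for one participant. Alternatively keep the title, replace the 100 mg column with about 0.001, 0.03 and 0.20 and the 50 mg, CV 50% cell with about 0.008 (any of 7, medians from Table 11). In either case qualify the sentence after the tables for CV 50%.
3. SAP 3.1 and the matching paragraph of protocol 9.5: replace the reference to an individual with at least one of the active participants planned at the next dose (6 in Part 1, 7 in Part 2).
4. Protocol 7.1.4 and SAP 3.1: state that for Cohort 6 the 96.2 limit applies to the maximum 24-hour AUC, together with Cmax 21 µg/mL.

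Table 15 needs no recomputation. The cost is two symbols, one table title or four cells, a few sentences and a check of existing code. No new data or redesign is needed.
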